9.5.4.2 Reporting of Pregnancy and Exposure to Study Drug Through Breastfeeding

Any pregnancy in which the estimated date of conception is either before the last visit or within 3 months of last study treatment or any exposure to study drug through breastfeeding during study treatment or within 3 months of last study treatment must be reported. (revised per Amendment 01)

If an adverse outcome of a pregnancy is suspected to be related to study drug exposure, this should be reported regardless of the length of time that has passed since the exposure to study treatment. Any pregnancy in which the estimated conception date is after using commercial BAN2401, reporting is not required as these events are collected separately as a spontaneous report. (revised per Amendment 18)

A congenital anomaly, death during perinatal period, an induced abortion, or a spontaneous abortion are considered to be an SAE and should be reported in the same time frame and in the same format as all other SAEs (see [Reporting of Serious Adverse Events \[Section 9.5.4.1\]](#)).

Pregnancies or exposure to study drug through breastfeeding must be reported by fax or email as soon as possible but no later than 1 business day from the date the investigator becomes aware of the pregnancy. The contact information for the reporting of pregnancies and exposure to study drug through breastfeeding is provided in the Investigator Study File. The Pregnancy Report Form must be used for reporting. All pregnancies must be followed to outcome. The outcome of the pregnancy must be reported as soon as possible but no later than 1 business day from the date the investigator becomes aware of the outcome.

A subject who becomes pregnant must be withdrawn from the study.

9.5.4.3 Reporting of Other Events of Interest

REPORTING OF ADVERSE EVENTS ASSOCIATED WITH STUDY DRUG OVERDOSE, MISUSE, ABUSE, OR MEDICATION ERROR

Adverse events associated with study drug overdose, misuse, abuse, and medication error refer to AEs associated with uses of the study drug outside of that specified by the protocol. Overdose, misuse, abuse, and medication error are defined as follows:

Overdose	Accidental or intentional use of the study drug in an amount higher than the protocol-defined dose
Misuse	Intentional and inappropriate use of study drug not in accordance with the protocol
Abuse	Sporadic or persistent intentional excessive use of study drug accompanied by harmful physical or psychological effects
Medication error	Any unintentional event that causes or leads to inappropriate study drug use or subject harm while the study drug is in the control of site personnel or the subject.

All AEs associated with an overdose should be captured on the Adverse Event eCRF. Adverse events associated with overdose, misuse, abuse, or medication error should be reported using the procedures detailed in Reporting of Serious Adverse Events ([Section 9.5.4.1](#)) even if the AEs do not meet serious criteria. Abuse is always to be captured as an AE. If the AE associated with an overdose, or medication error does not meet serious criteria, it must still be reported using the SAE form and in an expedited manner but should be noted as nonserious on the SAE form and the Adverse Event eCRF.

REPORTING OF SIGNIFICANT LABORATORY ABNORMALITY

Any significant treatment-emergent laboratory abnormality observed during the clinical study should be entered on the Adverse Event eCRF and reported using the procedures detailed in Reporting of Serious Adverse Events ([Section 9.5.4.1](#)), even if the laboratory abnormality does not meet serious criteria. If the significant laboratory abnormality does not meet serious criteria, it must still be reported using the SAE form and in an expedited manner but should be noted as nonserious on the SAE form and the Adverse Event eCRF.

A laboratory result should be considered a treatment-emergent significant abnormality if the result:

- Is within normal limits at baseline and has increased in severity to meet the sponsor's grading criteria for laboratory values of Grade 3 or above
- Is outside normal limits at baseline and increases in severity to the sponsor's grading criteria for laboratory values of Grade 4 or above.
- Is otherwise considered by the investigator to meet serious criteria as defined in [Section 9.5.1.5 \(Serious Adverse Events and Other Events of Interest\)](#)

Significant laboratory abnormalities should not be listed as separate AEs or SAEs if they are considered to be part of the clinical syndrome that is being reported as an AE or SAE.

REPORTING OF STUDY-SPECIFIC EVENTS

Study-specific events, including pregnancy, any treatment-emergent significant laboratory abnormality, and vasogenic edema (ARIA-E), macrohemorrhages, superficial siderosis, or new cerebral microhemorrhages on brain MRI, infusion reactions (any grade of severity as per NCI-CTCAE criteria), skin rash considered to be due to study drug, other hypersensitivity reactions, or a "yes" response to C-SSRS suicidal ideation type 4 or 5, an increase in body temperature to greater than 38°C within 24 hours postdose, or AEs associated with study drug overdose, or medication error, should be entered on the Adverse Event eCRF and reported using the procedures detailed in Reporting of Serious Adverse Events ([Section 9.5.4.1](#)), even if the study-specific event does not meet serious criteria. (revised per Amendment 08) If the event does not meet serious criteria, it must still be reported using the SAE form and in an expedited manner but should be noted as nonserious on the SAE form and the Adverse Event eCRF.

9.5.4.4 Expedited Reporting

The sponsor must inform investigators and regulatory authorities of reportable events, in compliance with applicable regulatory requirements, on an expedited basis (ie, within specific time

frames). For this reason, it is imperative that sites provide complete SAE information in the manner described above.

9.5.4.5 Breaking the Blind

In the case of a medical emergency where the appropriate treatment of the subject requires knowledge of the study treatment given, the investigator may break the randomization code for an individual subject. In all such cases, the AE necessitating the emergency blind break will be handled as an SAE in accordance with the procedures indicated above. Any broken code will be clearly justified and documented. The medical monitor must be notified immediately of the blind break.

9.5.4.6 Regulatory Reporting of Adverse Events

Adverse events will be reported by the sponsor or a third party acting on behalf of the sponsor to regulatory authorities in compliance with local and regional law and established guidance. The format of these reports will be dictated by the local and regional requirements.

All studies that are conducted within any European country will comply with European Good Clinical Practice Directive 2005/28/EC and Clinical Trial Directive 2001/20/EC. All suspected unexpected serious adverse reactions (SUSARs) will be reported, as required, to the competent authorities of all involved European member states.

9.5.5 Completion/Discontinuation of Subjects

A subject may elect to discontinue the study at any time for any reason. Subjects who discontinue the study or study drug early must comply with the Early Termination Visit (within 7 days after the last dose of study drug) and the Follow-Up Visit (3 months after the last dose of study drug). They may also have unscheduled visits for safety assessments. Subjects who discontinued the Core Study due to APOE status are expected to return for their Early Termination Visit and 3-month Follow-Up Visit (ie, 3 months after the last dose of study drug). In addition, subjects who discontinue from study drug are expected to return after the Early Termination Visit for each scheduled visit when the clinical assessments of efficacy are to be conducted (Visits 9, 16, 22, 29, 35, and 42) per the Schedule of Procedures/Assessments (Table 8). At these visits, clinical efficacy assessments (MMSE, CDR, ADAS-Cog, and FAQ) will be completed and information on concomitant medications, AEs, and SAEs will be collected from these subjects. Regularly scheduled clinical efficacy visits do not need to be attended if they fall within 8 days after the Early Termination Visit or within ± 8 days of the 3-month Follow-Up Visit. Subjects who complete the Core Study may elect to continue into the Extension Phase Part A if the criterion is met (see Appendix 4). Subjects who discontinue study drug in the Extension Phase will not be required to return after the Early Termination Visit for each scheduled visit when clinical efficacy assessments are conducted. Subjects in the Extension Phase who discontinue the study or study drug early are requested to undertake the Early Termination Visit (within 7 days after the last dose of study drug) and the Follow-Up Visit (3 months after the last dose of study drug). The 3-month Follow-Up Visit is not required for any subject who transitions directly from the Extension Phase Part A or Part B (including the postmarketing section in Japan) of the study to commercial BAN2401 (revised per Amendments 08, 11, 17, and 18). Upon approval of BAN2401 in Japan, subjects who meet the approved indication and dosage of BAN2401 will continue in Extension Phase Part A or

B of this study as a postmarketing part in Japan. Treatment will continue until BAN2401 is commercially available for individual subjects at each study site, at which time the subjects will switch to commercial BAN2401. For those subjects who transition to commercial BAN2401 (including the postmarketing section in Japan), the end of the study will be the date of the last study evaluation prior to transitioning to commercial BAN2401 and at which time, all assessments included in Week 261/Early Termination Visit (Part A) and Early Termination Visit (Part B) are to be performed according to the Schedule of Assessments of Part A and Part B, respectively. (revised per Amendments 18 and 19)

Subjects who discontinue from study drug are considered on study as long as they return for their regularly scheduled clinical efficacy visits as outlined above.

Subjects who discontinue due to AE will not be allowed to rescreen for the BAN2401-G000-201 study. Subjects who discontinue due to ARIA will be unblinded by the sponsor. (revised per Amendments 06 and 11)

The investigator will promptly explain to the subject involved that the study will be discontinued for that subject and provide appropriate medical treatment and other necessary measures for the subject. A subject who has ceased to return for visits will be followed up by mail, phone, or other means to gather information such as the reason for failure to return, the status of treatment compliance, the presence or absence of AEs, and clinical courses of signs and symptoms. This information will be recorded in the eCRF.

Subjects who discontinue early from the study will be discontinued for 1 of these primary reasons: AE(s), lost to follow-up, subject choice, withdrawal of consent, pregnancy, study terminated by sponsor, or other. In addition to the primary reason, the subject may indicate 1 or more of secondary reasons for discontinuation. Study disposition information will be collected on the Subject Disposition eCRF.

A subject removed from the study for any reason may not be replaced.

9.5.6 Abuse or Diversion of Study Drug

Not applicable. The study drug is to be administered by study site personnel.

9.5.7 Confirmation of Medical Care by Another Physician

The investigator will instruct subjects to inform site personnel when they are planning to receive medical care by another physician. At each visit, the investigator will ask the subject whether he/she has received medical care by another physician since the last visit or is planning to do so in the future. When the subject is going to receive medical care by another physician, the investigator, with the consent of the subject, will inform the other physician that the subject is participating in the clinical study.

9.6 DATA QUALITY ASSURANCE

This study will be organized, performed, and reported in compliance with the protocol, standard operating procedures, working practice documents, and applicable regulations and guidelines. Site

audits will be conducted periodically by the sponsor's or the CRO's qualified compliance auditing team, which is an independent function from the study team responsible for conduct of the study.

9.6.1 Data Collection

Data required by the protocol will be collected on the eCRFs, which constitute into a validated data management system that is compliant with all regulatory requirements. As defined by ICH guidelines, the eCRF is a printed, optical, or electronic document designed to record all of the protocol-required information to be reported to the sponsor on each study subject.

Data collection on the eCRF must follow the instructions described in the CRF Completion Guidelines. All activities, including remote assessments, must be documented with a clear description of how this is related to the COVID-19 pandemic (or other extenuating circumstances). The investigator has ultimate responsibility for the collection and reporting of all clinical data entered on the eCRF. The investigator or designee as identified on Form FDA 1572 (where applicable) must sign the completed eCRF to attest to its accuracy, authenticity, and completeness. (revised per Amendment 15)

Completed eCRF case books are the sole property of Eisai and should not be made available in any form to third parties without written permission from Eisai, except for authorized representatives of Eisai or appropriate regulatory authorities.

9.6.2 Clinical Data Management

All software applications used in the collection of data will be properly validated following standard computer system validation that is compliant with all regulatory requirements. All data, both CRF and external data (eg, laboratory data), will be entered into a clinical system.

9.7 STATISTICAL METHODS

All statistical analyses will be performed by the sponsor or designee after the database is locked and released for unblinding. (revised per Amendment 07) At each IA of the primary endpoint, a snapshot of the data will be obtained and released for analysis. A copy of this snapshot will be archived. This process will also be followed for the safety data that will be used for analysis for the DSMB. Statistical analyses will be performed using SAS software or other validated statistical software as required. All statistical tests will be based on the 10% level of significance, except for the Bayesian methods on the primary endpoint (revised per Amendments 09 and 10). Details of the statistical analyses will be included in a separate statistical analysis plan (SAP).

9.7.1 Statistical and Analytical Plans

The statistical analyses of the BAN2401-G000-201 study data are described in this section. Further details of the analysis plan will be provided in the SAP, which will be finalized before the first IA.

In this Phase 2 dose-finding study of BAN2401 for the treatment of EAD, response adaptive randomization will be used to allocate subjects to placebo control or 1 of the 5 active doses with the goal of characterizing the dose response. The study will be monitored for early success and early futility. The sponsor intends that the futility rule for stopping will be binding. If the study

continues to randomize subjects after futility is declared, it will be considered a failed study. (revised per Amendment 01)

9.7.1.1 Study Endpoints

PRIMARY ENDPOINT:

- Change from baseline in the ADCOMS at 12 months

KEY SECONDARY ENDPOINTS: (revised per Amendments 09 and 10)

- Change from baseline at 18 months in brain amyloid pathophysiology as measured by amyloid PET (revised per Amendments 09 and 10)
- Change from baseline in the ADCOMS at 18 months (revised per Amendment 09)
- Change from baseline in CDR-SB at 18 months (revised per Amendments 09 and 10)
- Change from baseline in ADAS-Cog at 18 months (revised per Amendments 09 and 10)
- Change from baseline in CSF biomarkers ($A\beta[1-42]$, t-tau, and p-tau) at 18 months (revised per Amendment 10)
- Change from baseline in total hippocampal volume at 18 months using vMRI (revised per Amendments 09 and 10)

SECONDARY ENDPOINTS: (revised per Amendments 09 and 10)

- Change from baseline at 12 months in brain amyloid pathophysiology as measured by amyloid PET (revised per Amendments 09 and 10)
- Change from baseline at 12 months on clinical status for the following assessments: ADCOMS, CDR-SB, and ADAS-Cog (revised per Amendment 10)
- Change from baseline in CSF biomarkers ($A\beta[1-42]$, t-tau, and p-tau) at 12 months (revised per Amendment 10)
- Change from baseline in total hippocampal at 6 and 12 months, and in left and right hippocampus, whole brain, and total ventricular volume as measured by vMRI at 6, 12, and 18 months (revised per Amendment 10)

EXPLORATORY ENDPOINTS:

- Change from baseline in clinical status at time points not analyzed in Key Secondary and Secondary sections for each of the following: ADCOMS, ADAS-Cog, CDR-SB, MMSE, and FAQ (revised per Amendment 10)

9.7.1.2 Definitions of Analysis Sets

The Randomized Set is the group of subjects who are randomized to study drug.

The Safety Analysis Set is the group of subjects who receive at least 1 dose of study drug and have at least 1 postdose safety assessment.

The Full Analysis Set is the group of randomized subjects who receive at least 1 dose of study drug and have baseline and at least 1 postdose primary efficacy measurement.

The PK Analysis Set is the group of subjects with at least 1 quantifiable BAN2401 serum concentration with a documented dosing history.

The PD Analysis Set is the group of subjects who have sufficient PD data to derive at least 1 PD parameter.

The Per Protocol (PP) Analysis Set is the subset of subjects in the Full Analysis Set who sufficiently complied with the protocol. The PP Analysis Set will be used to conduct a sensitivity analysis of the primary efficacy endpoint. Details of the evaluability criteria will be determined before database lock and treatment unblinding and will be specified in the SAP.

9.7.1.3 Subject Disposition

The number of subjects screened, the number (percent) of subjects who failed screening, and the reasons for screen failure will be summarized, based on data reported on the Screening Disposition eCRF. The distribution of the number of randomized subjects enrolled by each site will be summarized for each randomized treatment group. The primary reasons for screen failures; did not meet inclusion/exclusion criteria, AE, lost to follow-up, withdrawal consent, and other, will be presented.

Study Completion: the number (percent) of randomized and treated subjects who completed the study and who discontinued from the study will be summarized according to the primary reason for discontinuation and secondary reason(s) for discontinuation, based on data reported on the Subject Disposition (Study Phase) CRF. The number (percent) will be presented by treatment group and total for subjects; randomized, not treated, treated, who completed the study, and discontinued from the study. The primary reasons for discontinuation from the study are; AE, lost to follow-up, subject choice, withdrawal consent, pregnancy, study terminated by sponsor, and other. The secondary reasons for discontinuation from the study are: AE, subject choice, and other.

Completion of Study Treatment: the number (percent) of randomized and treated subjects who completed study treatment and who discontinued from study treatment will be summarized according to the primary reason for discontinuation and also according to secondary reason(s) for discontinuation, based on data reported on both the Subject Disposition (Study Phase) eCRF and Early Discontinuation from Study Drug eCRF. The number (percent) will be presented by treatment group and total for subjects; randomized, not treated, treated, who completed study treatment, and discontinued from study treatment. The primary reasons for discontinuation from the study treatment are: AE, lost to follow-up, subject choice, withdrawal of consent, pregnancy, study terminated by sponsor, inadequate therapeutic response, and other (revised per Amendment 01). The secondary reasons for discontinuation from the study are: AE, subject choice, and other.

9.7.1.4 Demographic and Other Baseline Characteristics

Demographic and baseline characteristics for the Safety Analysis set and Full Analysis set will be summarized for each treatment group using descriptive statistics. Continuous demographic and baseline variables include age, WMS-IV LMII, Geriatric Depression scale, MMSE; categorical variables include age ≤ 65 years, age > 65 years, sex, race, ethnicity, CDR score, memory box score of the CDR, positive amyloid load, *APOE4* genotype and clinical subgroup (MCI due to AD – intermediate likelihood or mild Alzheimer’s disease dementia).

9.7.1.5 Prior and Concomitant Therapy

All investigator terms for medications recorded in the eCRF will be coded to an 11-digit code using the World Health Organization Drug Dictionary. The number (percentage) of subjects who took prior and concomitant medications will be summarized on the Safety Analysis Set by treatment group, Anatomical Therapeutic Chemical (ATC), and the World Health Organization Drug Dictionary preferred term. Prior medications are defined as medications that stopped before the first dose of study drug. Concomitant medications are defined as medications that (1) started before the first dose of study drug and were continuing at the time of the first dose of study drug, or (2) started on or after the date of the first dose of study drug and continued up to the last dose.

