9.4.7.2 Core Study Prohibited Concomitant Therapies and Drugs

Anticoagulants (eg, warfarin, dabigatran) are not permitted for -7 days or 5 half-lives, whichever is longer, before Baseline until the Follow-Up Visit ([Appendix 2, Listing 1](#)). (revised per Amendment 01). Subjects who need to start chronic (>4 weeks) anticoagulant treatment during the study for concomitant diseases will be withdrawn from study drug. However, short-term (<4 weeks) treatment with anticoagulants is permitted for randomized subjects who undergo procedures requiring anticoagulants for prophylaxis of thromboembolic disease after approval by the sponsor's medical monitor. While these subjects need not be discontinued, study drug will be temporarily suspended during anticoagulant therapy. (revised per Amendment 06)

Immunoglobulin therapy and therapy with biologic drugs are not permitted for 6 months prior to the Baseline until the Follow-Up Visit. (revised per Amendment 01)

Subjects who are on AChEIs or memantine or both are required to be on a stable dose for 12 weeks before Baseline. During the study, if a subject starts, changes dose, or stops any of these medications, the subject will continue with study visits and assessments to study completion but the data from that subject will be censored as described in [Section 9.7.1.6](#). Use of memantine will not be allowed for Japanese subjects (revised per Amendments 01 and 07).

Medications which are used as needed (PRN) or as short courses of treatment and which are central nervous system-active and may affect cognitive function are not permitted during a period of 72 hours prior to cognitive testing ([Appendix 2, Listing 3](#)).

Subjects who are taking other medications will be required to be on a stable dose for at least 4 weeks prior to Baseline, except for medications which are administered as short courses of treatment (eg, anti-infectives) or which are to be used PRN. (revised per Amendment 01) During the study, subjects who initiate treatment with drugs not intended for treatment of cognitive impairment during the study or who change the doses of such drugs may continue in the study if in the opinion of the PI these drugs will not interfere with study procedures or subject safety and are not prohibited above. However, if such drugs may affect cognitive function, subjects should not undertake cognitive assessments until they have been on a stable dose for at least 4 week.

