Appendix 2 List of Permitted and Prohibited Prior/Concomitant Medications

Restricted medications are listed in [Listing #1](#). Medications that are permitted with restrictions are listed in [Listings #2, #3, and #4](#). (revised per Amendment 12)

These listings of restricted and permitted medications may not be all-inclusive listings. Please contact the medical monitor(s) if the investigators have any questions or concerns regarding any medication not listed that your subjects may be taking before enrollment or start during the course of the BAN2401-A001-201 study. (revised per Amendment 12)

Antibiotics, analgesics and anti-inflammatory drugs intended for short courses of treatment are permitted and do not need to follow the restrictions of [Listing #4](#) for a stable dose of 4 weeks prior to Baseline. If these medications may affect cognitive function but the medications are clinically indicated, then cognitive testing should not take place until at least 72 hours after the last dose of the course of treatment.

Postrandomization, subjects who require anticoagulant treatment as prophylaxis for ≤ 4 weeks need not be withdrawn if during this period study drug treatment is suspended, after discussion with sponsor medical monitor. See Listing 1 below for a list of restricted medications. (revised per Amendments 01, 06, and 12)

Listing 1 Restricted Medications Within 4 Weeks Prior to Extension Baseline (Extension Screening Visit) Until Follow-Up Visit

Generic Name	Trade Name
Anticoagulants (See Appendix 4 for Anticoagulant use during Extension Phase)	
Warfarin	Coumadin®, Jantoven
Dabigatran	Pradaxa
Enoxaparin	Lovenox
Dalteparin	Fragmin
Anisindione	Miradon
Tinzaparin	Innohep
Andeparin sodium	Normiflo
Heparin Sodium	Hemochron
Bivalirudin	Angiomax
Argatroban	
Rivaroxaban	Xarelto
Apixaban	Eliquis
Endoxaban	Savaysa
Lepirudin	Refludan
Fondaparinux	Arixtra®
Antithrombin III	ATryn, Thrombate III
Thrombolytics are permitted; however, treatment with study drug should be temporarily suspended during thrombolytic therapy until stabilization or resolution of the medical condition that required thrombolytic drug treatment (thrombolytic examples below).	
Streptokinase	Streptase
Reteplase	Retavase, Retevase
Tenecteplase	TNKase
Urokinase	Abbokinase, Kinlytic
Alteplase, tPA	Activase, Cathflo Activase
Antiplatelet drugs are permitted but the subject should be on a stable dose for 4 weeks before Extension Baseline (Extension Screening Visit).	

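### The concomitant-medication definition requires a drug started on study to run until the last dose, so short courses begun and ended during dosing fall outside the by-arm medication summary

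*Protocol*

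**What the plan says.** Section 9.7.1.5 sorts medications into two classes. For the first: "Prior medications are defined as medications that stopped before the first dose of study drug". The second, concomitant medications, has two parts. Part (1) takes drugs that "started before the first dose of study drug and were continuing at the time of the first dose of study drug". Part (2) takes drugs that "started on or after the date of the first dose of study drug and continued up to the last dose". The output is described in the same section: "The number (percentage) of subjects who took prior and concomitant medications will be summarized on the Safety Analysis Set", by treatment group, ATC class and preferred term.

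Elsewhere the protocol expects short courses on study. Section 9.4.7.2 says that "short-term (<4 weeks) treatment with anticoagulants is permitted for randomized subjects who undergo procedures requiring anticoagulants", and that "study drug will be temporarily suspended during anticoagulant therapy". Appendix 2 adds: "Antibiotics, analgesics and anti-inflammatory drugs intended for short courses of treatment are permitted". Section 9.4.7 has every medication given from informed consent onward recorded on the eCRF. No other section restates or corrects the definition in Section 9.7.1.5.

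**The concern.** Part (2) joins two conditions: the drug starts on study, and it is still being taken at the last dose. A two-week course begun at Week 20 meets the first condition and fails the second. It is not a prior medication either, because it did not stop before the first dose. It therefore belongs to no class and enters no summary that the protocol describes.

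Part (1) has no such end condition. A drug begun the day before the first dose and stopped a week later is counted; the same week of treatment begun a day after the first dose is not. The protocol gives no reason for the difference.

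What is at stake is how faithfully the table shows on-study medication by arm. Anticoagulant use matters most here: the revision history for Amendment 06 gives the risk of CNS hemorrhage from combining anticoagulant and study drug as the reason for the suspension provision. A table programmed to the stated rule would leave out the very courses that provision covers.

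**Working it through.** The protocol gives no figure on this point, so there is none to reproduce. The check is a reading of the rule followed by a size calculation.

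**Anticoagulant courses.** Study drug is suspended while the anticoagulant is given, so no dose falls within the course. There are two cases:
- Dosing resumes afterwards. The last dose then comes after the course has ended, so the course did not continue up to it.
- Dosing does not resume. The last dose then came before the course began, so again the course did not continue up to it.

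Part (2) fails in both cases, apart from ties on a single calendar date. Exclusion is essentially 100%.

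**Other short courses.** Inputs:
- First dose: Visit 3, Week 1 (Table 8, Panel A).
- Last infusion: Visit 41, Week 77 (Table 8, Panel B); footnote d confirms that Visits 42 and 43 have no infusion.
- Span: (77 − 1) × 7 = 532 days, or 533 calendar days counting both ends.
- Assumptions, not in the document: a course of L days starts on a day uniformly distributed over those 533 days, and the subject completes dosing.

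A course meets part (2) only if it is running on the last dose date, which holds for L of the 533 possible start days. Share counted = L / 533; share excluded = 1 − L / 533.

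| Course length L (days) | Counted | Excluded |
|---|---|---|
| 3 | 3/533 = 0.6% | 99.4% |
| 7 | 7/533 = 1.3% | 98.7% |
| 14 | 14/533 = 2.6% | 97.4% |
| 21 | 21/533 = 3.9% | 96.1% |
| 27 | 27/533 = 5.1% | 94.9% |
| 28 | 28/533 = 5.3% | 94.7% |

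**Sensitivity to early stopping.** The share counted rises as the dosing span shortens. For a subject whose last dose is at Week 27, the span is (27 − 1) × 7 + 1 = 183 calendar days. A 14-day course is then excluded with probability 1 − 14/183 = 92.3%, and a 27-day course with probability 1 − 27/183 = 85.2%.

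**Unit.** These are shares of courses. The table reports subjects by preferred term. A subject who was already taking the same drug at the first dose is counted through part (1), and one with a repeat course running at the last dose is counted through part (2). The subject-level loss is therefore smaller. Computing it would need the number, timing and overlap of courses per subject, which the protocol does not give.

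**The case against.** The strongest reply is that the wording is a slip. The authors probably meant to close the window at the last dose, and the rest of the protocol uses the word concomitant broadly: Section 9.4.7 records all medication on one form, and Section 9.4.7.2 treats short anticoagulant courses as concomitant therapy. A sensible programmer might read it that way, and the SAP, which is not available here, may already do so. That is plausible as to intent, but it does not repair the text. The protocol chose to state the definition, and a SAP that follows it inherits the gap while one that departs from it conflicts with it.

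It can also be said that little depends on this. The Core Study was complete by Amendment 11, the data are on the eCRF, and no test or decision rule uses the definition. This stands, and it limits the weight of the point.

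A reader might infer more than the document supports in four ways:
- **That on-study AD drug starts would largely vanish and the table would contradict the censoring counts.** An AChEI or memantine begun on study and still taken at the last dose meets part (2). Subjects censored for a dose adjustment were already on the drug at randomization, so part (1) counts them if they were still taking it at the first dose. The censoring rule in Section 9.7.1.6 does not use this definition. A count of users would not match a count of censored subjects even with correct wording, because it includes stable users.
- **That treatment of infusion reactions would be lost.** Under Section 9.5.1.5, Grade 3 and 4 reactions end study drug, so their acute treatment falls at about the last dose and may qualify. Reactions of every grade are also reported as events of interest.
- **That 95% to 99% of subjects would be missed.** That range applies to courses, not subjects.
- **That drugs begun after the last dose are wrongly left out.** Closing the on-treatment window at the last dose is an ordinary convention. A separate off-drug category would be an optional addition.

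**Conclusion.** The definition in Section 9.7.1.5 is wrong as worded: medications started and stopped within the dosing period fall into neither class. Permitted anticoagulant courses with study drug suspended are essentially always excluded, which follows from the text without any distributional assumption. For other courses of 4 weeks or less, about 95% to 99% are excluded per course, assuming uniform start dates and full completion of dosing; the share is lower in subjects who stop early. The effect on the tabulated subject percentages is smaller and is not known. The consequence is an understated descriptive medication table and nothing beyond it. This is a minor point, but a real error that costs little to correct.

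**What to change.** Reword part (2) of the definition so that it covers any medication with a start date from the date of the first dose of study drug through the date of the last dose, both inclusive, regardless of when it stopped. All courses that begin in the dosing period then count, and part (1) stays as it is. Check that the SAP and the table programming use the same rule.

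The cost is one clause in the protocol, and in the SAP if it carries the same wording. No new data are needed, because all medications are already recorded on the eCRF. If the Core table has already been produced under the literal rule, it would have to be rerun.
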